### **Cr Release CTL Assay (Patients with Evidence of Positive Tetramer and IFN- $\gamma$ ELISPOT Responses)**

3 X 10^6 cells/well in a 24 well plate will be in vitro pulsed for 7 days in the presence of the following conditions:

- 1) 10  $\mu$ M of the TARP 27-35 peptide (Native/WT peptide)
- 2) 10  $\mu$ M of the TARP 29-37-9V peptide (Epitope Enhanced Peptide)
- 3)  $\square\square\square\square$  flu matrix peptide (lower concentration due to potent stimulation peptide).

On day one 1000 U/ml IL-7 will be added and on day three cultures will be supplemented with 20 IU IL-2/ml. On day 7, cells will be harvested and plated to result in fixed effector to target cell ratios. Cells initially cultured with native or epitope enhanced TARP peptides will be tested against targets pulsed with 50  $\mu$ M of their respective TARP peptide, 50  $\mu$ M of TAX negative control peptide, and 50  $\mu$ M of CEF positive control peptide. Cells initially cultured with flu matrix peptide will be tested against targets pulsed with 1  $\mu$ M flu matrix peptide and 50  $\mu$ M of TAX negative control peptide, and 50  $\mu$ M of CEF positive control peptide. Targets will be labeled with 150  $\mu$ Ci [Cr] sodium dichromate. All target cells will then be washed three times and 3,000 labeled targets aliquoted into each well in a 96-well tissue culture plate that has already been plated with effector cells. At this point, both the effector and target cells will be suspended in complete T cell medium with 10% fetal calf serum and with a 10 fold excess of K562s (over targets). The plate will be incubated at 37° C for four hours. Supernatants will be harvested using a Skatron supernatant harvesting device and the samples counted on a gamma counter. Spontaneous release values will be obtained by incubating targets alone and maximum release values obtained by lysing the targets with Triton X-100.

The percent specific lysis is determined, on triplicate samples, by the following formula: percent specific lysis = 100 X (experimental release - spontaneous release)/(maximum release -

spontaneous release). The percent specific lysis of targets with TARP and control peptide will be compared to the percent specific lysis of targets without peptide. If these are significantly different using student's t test and if there is a greater than 10% difference at more than one effector:target ratio, we will consider the CTL assay to be positive.

NOTE Regarding Immunologic Response Testing: Assays will be run in batch for specimens from weeks 0, 12, 18 and 24. Samples with reactivity at week 24 will be used as a comparator control for batch assays for specimens run from weeks 36, 48, 60 and 96.

### **Restimulation Assay Following Apheresis at Weeks 0, 24, 48 and 96 (All Patients)**

The restimulation assay will be performed by the lab of Cell Mediated Immunity at NCI Frederick. Once apheresis is collected, *prior to monocyte elutriation* (week 0 only), 10 ml of apheresed PBMCs should be sent to the NCI Frederick Clinical Support Laboratory for processing. These cells will be placed in a three week cytotoxicity assay in which they are stimulated repeatedly with the mixture of TARP peptides with which they were vaccinated and flu matrix peptides as a control. A fraction will also be cryopreserved for future immunologic assays. Following these repeated stimulations, cells will then be tested on targets pulsed with each of these three peptides and on HLA A2.1 positive tumor cells expressing TARP.

### **Lymphocyte Subsets for FACS Analysis**

Peripheral blood mononuclear cells will be tested for the following markers via flow cytometry; CD3, CD4, CD8, CD3-/CD16/56+, CD3+/CD16/CD56+. Additional testing will be done on all patients in the research laboratory. We plan to use these markers to determine whether vaccination has caused a change in the number of these cells circulating in the peripheral blood and in the expression of cell surface markers. This assay will require three purple top tubes.

### **Multiparameter Flow Cytometric Analysis of NKT Cells**

Analysis will be performed by the laboratory of [name]. NKT cells will be identified by multiparameter flow cytometry. Markers may include, but are not limited to, Va24, Vb11, CD3, CD1d tetramer, CD4, CD8, and Hoechst 33258 for identification of viable cells. If sample permits, PBMC may be placed in culture for NKT cell activation, i.e. with  $\alpha$ -galactosylceramide, incubated at 37°C, and intracellular cytokines such as IFN- $\gamma$ , IL-4, IL-13 may be evaluated using multiparameter flow cytometry. If sample permits, immune cell subsets that contribute to regulation of the NKT axis, i.e. Tregs, may be analyzed.

#### ***When the blood is drawn:***

Please label the tubes including week number  
Contact the [name] lab at [contact]

***Abbreviated Title: TARP Peptide Vaccine Prostate Cancer  
CC Protocol 09-C-0139 L, Version Date: 01/10/2019***

Leave the blood for pickup at room temperature in the soiled utility room, in a container labeled "[name] Lab".

*Appendix 5B Guidelines and Worksheets for Calculation of PSADT*

**Calculated Pre-Enrollment/Baseline PSADT (in months):** \_\_\_\_\_

**PSADT Response is Defined As:**

- A  $\geq 50\%$  increase over baseline PSADT OR
- A PSADT > 15 months

PSADT Response will be assessed at weeks 12, 24, 36, 48, 60, 72, 84, 96, 108, 120, 132, 144.

On Study PSADT Calculated at Weeks 12, 24, 36, 48, 60, 72, 84, 96, 108, 120, 132, 144					
DATE	STUDY WEEK	PSA ng/mL	TESTOSTERONE ng/dL	Calculated PSADT	PSADT Responder?
	0				
	3				
	6				
	9				
	12				
	15				
	18				
	24				
	36				
	48				
	60				
	72				
	84				
	96				
	108				
	120				
	132				
	144				

**Record PSA values with a maximum of 2 digits after the decimal point.**

On Study Sequential PSADT Calculated for Statistical Analysis			
Analysis Window	Study Wk PSA Values Included	Calculated PSADT/Slope Log	Percent Change PSADT
Pre-NIH	Outside PSAs -12 Months to Entry		
-12Months to Week 3	-12 Months plus Wks 0, 3		
Week 0 to Week 3	NIH PSAs only Wks 0, 3		
Week 3 to Week 12	Wks 3, 6, 9, 12		
Week 3 to Week 24	Wks 3, 6, 9, 12, 15, 18, 24		
Week 3 to Week 48	Wks 3, 6, 9, 12, 15, 18, 24, 36, 48		
Week 24 to Week 48	Wks 24, 36, 48		
Week 48 to Week 72	Wks 48, 60, 72		
Week 48 to Week 96	Wks 48, 60, 84, 72, 96		
Week 96 to Week 120	Wks 96, 108, 120		
Week 96 to Week 144	Wks 96, 108, 120, 144		

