### 5.2.2 PSADT Response Criteria

PSADT was chosen as a surrogate marker for biochemical response to vaccination based on the Prostate-Specific Antigen Working Group's consensus Guidelines on PSADT. Utilization of PSADT as a predictive factor of disease progression and prostate cancer death is based on level II evidence derived from cohort- or case-controlled analytic studies or controlled, non-randomized trials that have been validated in multiple data sets, PSADT will be calculated using the Memorial Sloan-Kettering Cancer Center cancer information prostate nomogram for PSA doubling time found at:

<http://www.mskcc.org/mskcc/shared/forms/Nomograms/flash/load.cfm?type=Prostate&width=586&height=505&title=Prostate%20Nomogram> recommended in the Prostate Specific Antigen Working Group Guidelines. The PSADT is calculated assuming an exponential increase in serum PSA and first order kinetics. The formula takes into account the natural logarithm of 2 divided by the slope obtained from fitting a linear regression of the natural log of PSA on time. All PSA values used in the calculation should be 0.20 ng/ml or greater and follow an increasing trend. PSA values need not be consecutively increasing and all values obtained during a maximum period of 12 months prior to a given protocol time point will be included in the calculation. The maximum period of the last 12 months is recommended to reflect current disease activity because in some men PSADT may change over time. Multiple studies concur that men with a PSADT < 3 months are at extremely high risk for metastatic disease progression

and death with prostate cancer mortality approaching 100%; for this reason they have been excluded from participation in this study. In contrast, men with a slow PSADT i.e. > 15 months have an extremely low risk of death from prostate cancer.

The following general guidelines regarding PSA determinations and calculation of PSADT used in this protocol will be adhered to (refer to [Appendix 5](#), PSADT Calculation Guidelines)

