#### **Pre-Enrollment/Baseline and On Study PSADT:**

- PSADT will be calculated using the Memorial Sloan-Kettering Cancer Center cancer information prostate nomogram for PSA doubling time found at:  
<http://www.mskcc.org/mskcc/shared/forms/Nomograms/flash/load.cfm?type=Prostate&width=586&height=505&title=Prostate%20Nomogram>
- Minimum requirements for PSADT include  $\geq 3$  PSA measurements over  $\geq 3$  months.
- The interval between PSA measurements must be  $\geq 4$  weeks.
- For patients receiving 5-alpha reductase inhibitors (5ARI) e.g. finasteride or dutasteride, only PSA values obtained after at least 3 months on therapy may be used to calculate PSADT.
- Calculated PSADT values will be reported in months
- The same laboratory must have performed PSA values used in the calculation of PSADT.
- All PSA values used in the calculation should be  $\geq 0.20$  ng/mL and follow a rising trend although all values need not be consecutively rising.
- All values obtained over a maximum period of 12 months prior to any given protocol time point assessment should be included in the PSADT calculation to reflect the patient's current disease activity.
- PSA values obtained within  $\leq 2$  weeks of instrumentation, documented infection (prostatitis), or radiation proctopathy should be *omitted* from inclusion in PSADT calculations.

On Study PSADT will be calculated at baseline and weeks 12, 24, 36, 48, 60, 72, 84, 96, 108, 120, 132, and 144.

Exploratory comparisons of percent change in PSADT will be done among the following time points:

- Pre-Enrollment/Baseline PSADT vs. Week 3-12 PSADT/
- Pre-Enrollment/Baseline PSADT vs. Week 24 PSADT
- Pre-Enrollment/Baseline PSADT vs. Week 36 PSADT
- Pre-Enrollment/Baseline PSADT vs. Week 48 PSADT
- Week 24 PSADT vs. Week 36 PSADT
- Week 36 PSADT vs. Week 48 PSADT
- Additional exploratory analyses of PSADT will be performed of Pre-Enrollment/Baseline PSADT vs. Weeks 60, 72 and 96 and Week 48 PSADT vs. Weeks 96, 108 and 144 PSADT.

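### Several Appendix 5B PSADT windows conflict with the rules of Section 5.2.2, and two of those rules conflict with each other at weeks 12 to 36

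*Combined protocol and SAP*

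**What the plan says.** Section 5.2.2 states that the general guidelines "regarding PSA determinations and calculation of PSADT used in this protocol will be adhered to", and points to Appendix 5. Under a heading that covers both baseline and on-study PSADT it gives four relevant rules:

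- Number and span: "Minimum requirements for PSADT include" at least 3 PSAs over at least 3 months.
- Spacing: "The interval between PSA measurements must be" at least 4 weeks.
- Laboratory: "The same laboratory must have performed PSA values used in the calculation of PSADT".
- Look-back: "All values obtained over a maximum period of 12 months prior to any given protocol time point assessment should be included".

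The second table of Appendix 5B, headed as the sequential PSADT for statistical analysis, lists eleven windows. The first row takes outside PSAs from the 12 months before entry. The second adds weeks 0 and 3 to that period (minus "12 Months plus Wks 0, 3"). The third, "Week 0 to Week 3", uses NIH values only. The last row, for weeks 96 to 144, lists "Wks 96, 108, 120, 144".

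PSA is scheduled at week 132 in Section 3.4.2 and Appendix 1. Week 132 is a PSADT time point in Sections 3.1 and 5.2.2 and in the first Appendix 5B table. Section 5.2.2.1 assesses PSADT response (a rise of at least 50%, or a PSADT above 15 months) at week 12 and every later PSADT time point.

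**The concern.** There are two separate problems.

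The first is the Appendix 5B table. An analyst who follows it will compute PSADTs that Section 5.2.2 rules out, and no exemption appears in the text available.

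The second lies within Section 5.2.2 and affects the response endpoint. At weeks 12, 24 and 36 a 12-month look-back reaches back before study entry. If those PSAs came from another laboratory, the look-back rule brings them in and the one-laboratory rule keeps them out. No precedence is stated. A calibration difference between laboratories then enters the slope as a step at study entry. Response is judged within patients against baseline, so randomization does not remove it. The effect of vaccination on PSADT is secondary objective 1.1.2.1.

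**Working it through.** The plan gives no figure to reproduce here, so the check is of internal consistency, followed by the size of effect under stated assumptions.

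**1. Windows against rules.** Weeks are converted at 52.18/12 = 4.348 per month, using nominal visit weeks.

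| Window (weeks) | PSAs | Span (months) | Smallest gap (weeks) | Conflict |
|---|---|---|---|---|
| -12 months to 3 | varies | about 12.7 | 3 | laboratory (if earlier PSAs are outside), spacing |
| 0-3 | 2 | 0.69 | 3 | number, span, spacing |
| 3-12 | 4 | 2.07 | 3 | span, spacing |
| 3-24 | 7 | 4.83 | 3 | spacing |
| 3-48 | 9 | 10.35 | 3 | spacing |
| 24-48, 48-72, 96-120 | 3 each | 5.52 | 12 | none on number, span or spacing |
| 48-96 | 5 | 11.04 | 12 | none |
| 96-144 | 4 | 11.04 | 12 | scheduled week 132 left out |

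The three 24-week rows leave out earlier PSAs within 12 months. I do not count that, since 12 months is stated as a maximum.

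**2. Week 132.** SE(slope) = s/sqrt(Sxx), where s is the residual SD of ln PSA.
- Weeks 96, 108, 120, 144 (mean 117): Sxx = 441 + 81 + 9 + 729 = 1260.
- With week 132 (mean 120): Sxx = 576 + 144 + 0 + 144 + 576 = 1440.
- SE ratio = sqrt(1440/1260) = 1.069.

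**3. Week 0-3 row.** Sxx = 0.69²/2 = 0.238, so SE = 2.05 s per month. For assumed s of 5%, 10% and 15%, SE is 0.10, 0.20 and 0.31. The true slope at a PSADT of 9 months is ln 2/9 = 0.077. With no change in the disease, the fitted slope would be zero or negative in 23%, 35% and 40% of patients.

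**4. The two rules within Section 5.2.2.** Assumptions, none in the documents: quarterly outside PSAs, a step b between laboratories at study entry, all PSAs in the look-back used, and a baseline PSADT that reads true. Fitted slope = ln 2/D + k ln(1+b), where D is the true PSADT and k is the slope of an NIH indicator regressed on time.

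Week 12 uses -9, -6 and -3 months plus weeks 0, 3, 6, 9 and 12. The mean time is -1.388 months, Sxx = 124.9, and the NIH deviations sum to 13.84, so k = 13.84/124.9 = 0.111 per month. The slope shift is 0.111 × ln 0.9 = -0.0117 for NIH 10% lower and 0.111 × ln 0.8 = -0.0247 for 20% lower.

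| True PSADT (months) | True slope | Reads, NIH 10% lower | Reads, NIH 20% lower |
|---|---|---|---|
| 6 | 0.1155 | 6.7 (+11%) | 7.6 (+27%) |
| 9 | 0.0770 | 10.6 (+18%) | 13.3 (+47%) |
| 12 | 0.0578 | 15.0 (+25%) | 21.0 (+75%) |

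- At 10% lower, a false response needs ln 2/D < ln 2/15 + 0.0117 = 0.0579, so D above about 12.0 months.
- At 20% lower, the 50% rule is met when 0.0247 is at least one third of ln 2/D, so D of about 9.3 months or more.
- A step of 5% lower takes 12 months to 13.3, which is no response.
- If NIH reads 10-20% higher, 12 months reads 10.2-8.9.
- At week 24 (outside PSAs at -6 and -3 months, k = 0.105), 12 months reads 14.8-20.2 for NIH 10-20% lower.
- At week 36 (outside PSA at -3 months only, k = 0.063), it reads 13.6-15.9.

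**5. When NIH values alone suffice.** From week 0, week 12 spans 12/4.348 = 2.76 months, short of 3. Week 24 spans 5.52 months, and weeks 0, 6, 12, 18 and 24 also satisfy the 4-week spacing.

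**The case against.** The best defence is that the Appendix 5B table decides nothing. Section 6.2 refers the response endpoint to Section 5.2.2 and the exploratory comparisons to Sections 3.1 and 5.2.2. Response is recorded on a different worksheet, which includes week 132. This stands, and it limits severity. The table is still headed for statistical analysis.

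A reader might infer that the row adding weeks 0 and 3 turns a laboratory shift into an apparent vaccine effect. The documents do not support that. The row ends at week 3, when the first vaccine dose is given, and the laboratory change falls at study entry. The post-vaccination rows of the table use study-visit PSAs only. A reader might also attribute the 15.0 and 21.0 month figures to Appendix 5B. They come from the look-back rule of Section 5.2.2.

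The mixing of laboratories is itself inferred from the labels of the neighbouring rows. A patient whose earlier PSAs were all measured at NIH breaks no rule.

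It can be argued that Section 5.2.2 already sets an order, because one laboratory is a must and all values is a should. That is only partly right: the running text of the same section says that all values in the 12 months will be included.

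The two-point row may be meant only as a slope, as its column heading allows. The 3-week gaps are nominal, since visits may move by a week and Appendix 1 shows no PSA in the week 0 columns. Neither point brings the week 0-3 row up to 3 values or 3 months. Finally, the part of Appendix 5 before 5B was not available, so an exception stated there cannot be excluded.

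**Conclusion.** The concern holds as two inconsistencies.

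- Five Appendix 5B windows (-12 months to week 3, 0-3, 3-12, 3-24 and 3-48) conflict with the number, span, spacing or laboratory rules. A sixth omits a scheduled PSA, at a cost of a 7% wider slope SE.
- The look-back and one-laboratory rules of Section 5.2.2 cannot both be met at weeks 12, 24 and 36 for patients with outside pre-entry PSAs.

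The size of the second rests on an assumed laboratory step and assumed PSA dates. At week 12 with NIH 10-20% lower, a true 12 months reads 15.0-21.0. The values 9 and 6 months read 10.6-13.3 and 6.7-7.6, and neither meets the response definition. False responses are therefore confined to the upper part of the eligible range: above about 12 months at a 10% step, and from about 9.3 months at 20%.

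The documents do not support a claim that the primary analysis, the sample size or a Section 6 decision rule is affected. Severity is minor to moderate.

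**What to change.** 1. Add week 132 to the week 96-144 row of Appendix 5B.
2. State in Section 5.2.2 that the one-laboratory rule takes precedence over the all-values rule. On-study PSADT then uses NIH values only, once at least 3 values over at least 3 months exist. An earlier PSADT that mixes laboratories is flagged and not used to classify response in the analysis.
3. Report no PSADT from the week 0-3 row, or from the -12 months to week 3 row where it mixes laboratories. Delete these rows or label them descriptive.
4. State whether the 4-week and 3-month rules apply to the week 3-12, 3-24 and 3-48 windows, or exempt those windows explicitly with a reason.

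A laboratory term in the regression is not a good substitute. It still pools laboratories in one PSADT, and it does not fit the named nomogram, which regresses ln PSA on time alone.

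Week 24 PSADT response also feeds the extra-dose provision in Sections 3.1 and 5.2.2.1. The sponsor needs to reconcile that provision with whichever rule is adopted.

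The cost is text edits with no new data collection. The downside is fewer evaluable early PSADTs and lower precision. By the arithmetic above, NIH values from week 0 fall short of 3 months at week 12 but suffice by week 24.

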**Appendix 6: TARP Peptide Vaccination Report Card**

MEDICAL RECORD	Outpatient Progress Notes
-----------------------	----------------------------------

**TARP PEPTIDE DENDRITIC CELL VACCINE VACCINATION REPORT CARD**

Date/Time Vaccine Administered: \_\_\_\_\_ Administered By: \_\_\_\_\_

Protocol Week: \_\_\_\_\_ Vaccine Dose #: \_\_\_\_\_ Vaccine Cohort: \_\_\_\_\_

	Injection Volume (in ml)	# Cells / Injection	Arm B patients: ID Wheal Present?	DAY 1	DAY 2	DAY 3	DAY 4	DAY 5	Date resolved
Site #1				 0  1  2  3	 0  1  2  3	 0  1  2  3	 0  1  2  3	 0  1  2  3	
Site #2				 0  1  2  3	 0  1  2  3	 0  1  2  3	 0  1  2  3	 0  1  2  3	
Site #3				 0  1  2  3	 0  1  2  3	 0  1  2  3	 0  1  2  3	 0  1  2  3	
Site #4				 0  1  2  3	 0  1  2  3	 0  1  2  3	 0  1  2  3	 0  1  2  3	

Total Injection Volume: \_\_\_\_\_ Total Peptide-Pulsed Cells Delivered: \_\_\_\_\_

[figure not shown]
**Injection Site Reaction Grading (NCI CTCAE v3.0)**

0 No Reaction

1 Pain, itching or redness

2 Pain or swelling with significant inflammation (redness, tenderness or phlebitis)

3 Ulceration or necrosis (skin break down) that is severe; operative intervention indicated.

Outpatient Identification	Outpatient Progress Note NIH-532- 10 (8-00) P.A. 09-25-0099 File in Section 2: Progress Notes
---------------------------	---

## **Appendix 7: Exploratory Correlative Studies**

### **Measurement of Function-Associated mRNAs in Whole Blood: [name] Hitachi Chemical.**

To be performed on the last 10 subjects enrolled in the 09-C-0139 TARP vaccine study.

**Function-Associated mRNAs:** One 10ml green top sodium heparin tube  
**(Weeks 0, 12, 18 and 24)**

- Blood will be drawn into one 10ml green top tube.
- Add 60 µL each of blood into three 8-well strips (provided by [name]). Strips contain PHA, HAG, PBS, rIL2, rIFN $\alpha$ , CEF, LPS/ZA, TARP27-35 and TARP EE-29-37).
- Incubate at 37°C for 4 hours.
- Store in -80°C freezer until ready for shipment to [name]
- **Note: specimen should be drawn before 1pm** to allow adequate time for specimen processing and four hour incubation by [name] lab staff.
